**Table 10 Management of Specific Toxicities and Dose Modification Guidelines (cont.)**

Adverse Event	Action	
	3	Severe or medically significant but not immediately sight threatening; hospitalization or prolongation of existing hospitalization indicated; disabling; limiting self-care ADL
	4	Sight-threatening consequences; urgent intervention indicated; blindness (20/200 or worse) in the affected eye
	
Interrupt cobimetinib and vemurafenib.
 
Consult ophthalmology and undergo complete ophthalmologic examination, which includes visual acuity testing, intraocular pressure measurements by tonometry, slit-lamp ophthalmoscopy, indirect ophthalmoscopy, and spectral domain optical coherence tomography
 
If retinal vein occlusion (RVO) is diagnosed, vemurafenib and cobimetinib dosing should be permanently discontinued and RVO treated per institutional guidelines.
 
If neurosensory retinal detachment is diagnosed, cobimetinib dosing should be interrupted until symptoms improve to Grade 1. Then cobimetinib should be dose reduced by 1 dose level when restarting. If visual symptoms of Grade <math>\geq 2</math> recur despite 2 dose level reductions of cobimetinib, cobimetinib should be permanently discontinued. The patient may continue on study treatment with vemurafenib alone in the event that cobimetinib/placebo is discontinued.
 
If uveitis/iritis is diagnosed, Grade <math>\leq 2</math> uveitis/iritis can be managed with ophthalmologic input using local non-invasive therapies and/or short courses of systemic therapy. Dose reduction of study drugs is NOT required if uveitis/iritis is Grade <math>\leq 2</math>. For Grade <math>\geq 3</math> uveitis/iritis, vemurafenib should be reduced by 1 dose level.
 
If RVO, neurosensory retinal detachment or uveitis/iritis are NOT identified:
 
 
● and visual symptoms have not resolved to Grade 1 or less (with the continued use of local / non-invasive supportive care) within 28 days, permanent discontinuation of both study drugs should be considered.
 
● and visual symptoms have resolved to Grade 1 or less (with the continued use of local / non-invasive supportive care) within 28 days, resume use of vemurafenib and cobimetinib at current doses.
 
	

Table 10 Management of Specific Toxicities and Dose Modification Guidelines (cont.)	
Adverse Event	Action
	
 
If visual symptoms of Grade <math>\geq 2</math> (despite the optimal use of local / non-invasive supportive care) recur, vemurafenib and/or cobimetinib should be dose reduced by 1 level, depending on which agent is implicated. If visual symptoms of Grade <math>\geq 2</math> recurs despite 2 dose level reductions of both vemurafenib and cobimetinib, and maximal supportive care, vemurafenib and cobimetinib should be permanently discontinued.
 

E) Diarrhea Grade $>3$	
a) No change in vemurafenib and cobimetinib dosing will be implemented for Grade <math>\leq 2</math> diarrhea; patients should receive maximal supportive care.
 
b) If Grade <math>\geq 3</math> diarrhea occurs despite adequate supportive care, then both drugs should be held until the diarrhea has improved to Grade <math>\leq 1</math>.
 
 
If this occurs within 28 days, vemurafenib and cobimetinib may be restarted with cobimetinib reduced by 1 dose level, with continued supportive care or prophylaxis.
 
If bowel movement characteristics have NOT improved to Grade <math>\leq 1</math> or baseline with maximal supportive care by 28 days, then both drugs should be discontinued.
 
 
d) If Grade <math>\geq 3</math> diarrhea recurs despite supportive care and cobimetinib dose reduction, vemurafenib and cobimetinib should be held until the diarrhea resolves to Grade <math>\leq 1</math>. If this occurs within 28 days, then therapy may be re-initiated with vemurafenib reduced by 1 dose level. The cobimetinib dose will be maintained at the previously reduced dose.
 
e) If the diarrhea recurs at Grade <math>\geq 3</math> despite supportive care and dose reductions of 2 dose levels in both drugs (i.e., vemurafenib to 480 mg BID and cobimetinib to 20 mg QD), then both drugs should be permanently discontinued.

F) Rhabdomyolysis or CPK elevations	
Rhabdomyolysis or symptomatic CPK elevations: Interrupt cobimetinib treatment. If severity is improved by at least one grade within 4 weeks, restart cobimetinib at a dose reduced by 20 mg, if clinically indicated. Vemurafenib dosing can be continued when cobimetinib treatment is modified, if clinically indicated.
 
If rhabdomyolysis or symptomatic CPK elevation do not improve within 4 weeks, permanently discontinue cobimetinib treatment.
 
Asymptomatic CPK elevations:
 
Grade <math>\leq 3</math>: cobimetinib dosing does not need to be modified or interrupted to manage asymptomatic Grade <math>\leq 3</math> CPK elevations.
 
Grade 4: Interrupt cobimetinib treatment. If improved to

Table 10 Management of Specific Toxicities and Dose Modification Guidelines (cont.)	
Adverse Event	Action
	Grade ≤3 within 4 weeks, restart cobimetinib at a dose reduced by 20 mg, if clinically indicated. Vemurafenib dosing can be continued when cobimetinib treatment is modified, if clinically indicated. If CPK elevations do not improve to Grade ≤3 within 4 weeks following dose interruption, permanently discontinue cobimetinib treatment.
G) LFT elevations	
a) If Grade ≤2, continue current dose of vemurafenib and cobimetinib.
 
b) If Grade 3, hold vemurafenib. Continue current dose of cobimetinib. Upon resolution of LFT to Grade ≤1, resume vemurafenib at 1 lower dose level (e.g., 960 mg to 720 mg, or 720 mg to 480 mg).
 
c) If Grade 4, see Section J below.
 
d) No dose modification is required for isolated GGT elevation in the absence of clinically significant elevation above baseline grade in AST, ALT, ALP, bilirubin or hepatic.

H) QTcF interval prolongation on ECG Grade ≥ 3	
a) Rule out other risk factors for arrhythmia (e.g., myocardial ischemia); check for electrolyte disturbances (particularly potassium and magnesium levels) in all cases.
 
b) Evaluate concomitant medications to determine if there is co-administration of drugs that prolongs QTc interval in all cases (e.g., 5-HT3 receptor antagonist anti-emetics; see Appendix 9).
 
c) Interrupt dosing of vemurafenib ECG monitoring should be performed until QTc interval decreases below 500 ms. Electrolytes abnormalities should be corrected in all cases. Continue dosing with cobimetinib at the current dose if otherwise tolerated.
 
d) Plan to seek a cardiologist consultation or advice.
 
e) If QTc interval does not improve within 28 days after interruption of vemurafenib dosing, permanently discontinue vemurafenib; continue dosing with cobimetinib at the current dose.
 
f) If QTc improves within 28 days, restart dosing of vemurafenib at 1 reduced dose level.
 
g) Repeat 12-lead ECG monitoring at 2 weeks and 4 weeks of restarting vemurafenib at the lower dose. Additional ECG monitoring will be performed at Day 15 of each subsequent Cycle for 3 cycles, and every 3 months thereafter.
 
h) If second increase in QTc interval to > 500 ms occurs at the lower dose of vemurafenib, follow guidelines above, and reduce dose of vemurafenib by an additional dose level.
 
i) Permanently discontinue vemurafenib if after correction of associated risk factors and dose reductions, the QTc increase meets values of both > 500 ms and > 60 ms change from pre-treatment values.

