### 5.1.5.3 Management of Specific Toxicities and Dose Modification Guidelines

**Table 10 Management of Specific Toxicities and Dose Modification Guidelines**

Adverse Event	Action
A) Rash Grade $\geq 3$	
The appearance of rash must be characterized as acneiform or non-acneiform.
 
No change in vemurafenib and cobimetinib dosing will be implemented for Grade <math>\leq 2</math> rash; patients should receive maximal supportive care per institutional guidelines.
 
Acneiform rash
 
Hold cobimetinib dosing until Grade <math>\leq 2</math>.
 
Vemurafenib dosing may continue when cobimetinib is interrupted.
 
Reduce cobimetinib by 1 dose level. If after restarting at reduced dose, the patient experiences skin toxicity Grade <math>\geq 3</math>, further reduce cobimetinib by another dose level. Permanently discontinue cobimetinib if restarting after second dose reduction, the patient experiences skin toxicity Grade <math>\geq 3</math>.
 
Permanently discontinue cobimetinib if rash <math>\geq 3</math> persists for <math>> 28</math> days despite adequate supportive care.
 
Non-acneiform or maculo-papular rash
 
Delay vemurafenib dosing until Grade <math>\leq 2</math>.
 
Cobimetinib dosing may continue when vemurafenib is interrupted.
 
For Grade 3 rash, reduce vemurafenib by 1 dose level. If after restarting at reduced dose, the patient experiences skin toxicity Grade <math>\geq 3</math>, further reduce vemurafenib by 1 dose level.
 
Permanently discontinue vemurafenib if restarting after second dose reduction, the patient experiences recurrent skin toxicity Grade <math>\geq 3</math>.
 
For Grade 4 rash, reduce vemurafenib by 2 dose levels.
 
Permanently discontinue vemurafenib if after restarting at reduced dose, the patient experiences skin toxicity Grade <math>\geq 3</math>.

Table 10 Management of Specific Toxicities and Dose Modification Guidelines (cont.)							
Adverse Event	Action						

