B) Photosensitivity Grade $\geq 3$	
a) Grade <math>\leq 2</math> photosensitivity should be managed with supportive care and treatment of both vemurafenib and cobimetinib may be continued.
 
If Grade 2 photosensitivity does not resolve to Grade <math>\leq 1</math> after 7 days or if photosensitivity worsens to Grade <math>\geq 3</math> despite best supportive care, then both vemurafenib and cobimetinib treatment must be interrupted until the photosensitivity resolves to a Grade <math>\leq 1</math>.
 
b) If resolution to Grade <math>\leq 1</math> occurs within 28 days, treatment may be re-initiated with vemurafenib dose reduced by 1 level and without change in cobimetinib dose.
 
If the photosensitivity does not resolve to Grade <math>\leq 1</math> by 28 days, then the therapy with vemurafenib and cobimetinib should be discontinued.
 
c) If the photosensitivity recurs to Grade <math>\geq 3</math> with vemurafenib and cobimetinib, re-initiation despite prophylactic measures and dose reduction of vemurafenib, then both agents should be held until the photosensitivity resolves to Grade <math>\leq 1</math> or less. The dose of vemurafenib should be reduced by another dose level.
 
d) If photosensitivity recurs a second time to Grade <math>\geq 3</math> despite prophylactic measures and the aforementioned 2 dose reductions of vemurafenib, vemurafenib should be discontinued. The patient may continue on study treatment with cobimetinib/placebo alone.
						

C) New skin lesion, suggestive of any cutaneous primary malignancy.
 
Any cutaneous primary malignancy is considered a Grade 3 event in this study.
	
a) Follow SCC Risk Management Plan detailed in protocol
 
b) Interrupt vemurafenib and cobimetinib for 48 hours before and after excisional biopsy. This period of interruption may be altered based upon experience in this study.
 
c) If lesion is diagnosed as cuSCC, treatment may be re-instituted with vemurafenib and cobimetinib at pre-event dose levels after the lesion is excised. If the lesion is not excised, vemurafenib treatment must be discontinued.
 
d) If the lesion is not an SCC, then treatment with vemurafenib and cobimetinib may be restarted at the most recent dose level.
						

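### Table 10, row E (diarrhea): the stopping rule applies only at vemurafenib 480 mg and cobimetinib 20 mg, but no step in the row orders the second cobimetinib reduction needed to get there

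*Protocol*

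**What the plan says.** Table 9 (Protocol, Section 5.1.5) gives two reduced levels per drug: vemurafenib 720 then 480 mg BID, and cobimetinib 40 then 20 mg QD. The text below it makes each drug's reduction independent of the other's, forbids re-escalation and leaves room for clinical judgment.

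Row E of Table 10 (Section 5.1.5.3) is lettered a, b, d, e:

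- **Step a:** no dose change up to Grade 2.
- **Step b:** at Grade 3 or higher, hold both drugs. If there is improvement to Grade 1 or lower within 28 days, "vemurafenib and cobimetinib may be restarted with cobimetinib reduced by 1 dose level". If there is no such improvement "by 28 days, then both drugs should be discontinued".
- **Step d:** on recurrence "despite supportive care and cobimetinib dose reduction, vemurafenib and cobimetinib should be held until the diarrhea resolves". If that happens within 28 days, "therapy may be re-initiated with vemurafenib reduced by 1 dose level". It adds: "The cobimetinib dose will be maintained at the previously reduced dose".
- **Step e:** permanently discontinue both drugs if severe diarrhea recurs despite "dose reductions of 2 dose levels in both drugs (i.e., vemurafenib to 480 mg BID and cobimetinib to 20 mg QD").

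**The concern.** A stopping rule that names exact doses should be reachable through the steps leading up to it. Step e assumes two reductions in each drug. The steps before it order one cobimetinib reduction and then say that cobimetinib stays at that dose. Followed literally, they leave a patient with repeated severe diarrhea at a dose pair for which the row gives neither a further reduction nor a stop.

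Section 5.1.2.3 reports diarrhea as the most common adverse event in this trial. The table still governs patients on treatment, including control patients who cross over to cobimetinib (Section 3.1). What is at stake is consistent, safe dose management across sites. No efficacy result depends on it.

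**Working it through.** Doses are written as vemurafenib mg BID / cobimetinib mg QD.

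**Inputs.** The Arm B start is 960/60 (Section 3.1). The levels are 960, 720, 480 and 60, 40, 20 (Table 9). Step b means cobimetinib down one level. Step d means vemurafenib down one level with cobimetinib unchanged. Step e applies at 480/20.

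**The plan's own figure.** Two levels down from 960 is 480, and two levels down from 60 is 20. Step e's dose pair agrees with Table 9.

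**Walk from full dose, each episode resolving within 28 days:**

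| Severe episode | Step d applies once | Step d repeats |
|---|---|---|
| 1 | step b: 960/40 | step b: 960/40 |
| 2 | step d: 720/40 | step d: 720/40 |
| 3 | no step given | step d: 480/40 |
| 4 | – | no usable step (no vemurafenib level below 480) |

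Step e is met at neither 720/40 nor 480/40.

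**Count of one-level reductions.** Step e presupposes 2 + 2 = 4. The steps order 1 + 1 = 2 if step d applies once, or 2 + 1 = 3 if it repeats. The cobimetinib cut from 40 to 20 mg is missing on both readings.

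**Which sequences would reach 480/20?** Two uses of step b and two of step d are needed, starting with b: b-b-d-d, b-d-b-d or b-d-d-b. Each uses step b a second time, after cobimetinib has already been reduced. That is the situation step d describes, and step d says to maintain cobimetinib.

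**Starts below full dose because of another toxicity:**

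- 720/40: step b gives 720/20, then step d gives 480/20. Step e is reachable.
- 480/40: step b gives 480/20. Step e is reachable.
- 960/40: step b gives 960/20, then step d gives 720/20. Step e is reachable only if step d repeats.
- 480/60: step b gives 480/40. Step d then has no lower vemurafenib level, and step e is not met.

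**Other rows of Table 10.** Row A writes out the second cut ("further reduce cobimetinib by another dose level"). So does row B ("The dose of vemurafenib should be reduced by another dose level"), and row H does the same for vemurafenib. Row D leaves the second cobimetinib cut implicit, but has no sentence holding the dose. Row J is for other Grade 4 events and does not fill the gap.

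**How many patients.** Section 5.1.2.3 gives Grade 3 or 4 diarrhea in 6.5% of combination patients and 0.8% of control patients. Taking the 247 patients of Section 1.4.4 as the denominator (an assumption), 0.065 × 247 ≈ 16 had at least one such event. The gap needs three or four separate severe episodes in one patient, so the number reaching it should be well below 16.

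**The case against.** The strongest reply is that the row is under-specified and does not contradict itself. Step b is worded generally, and the sentence about maintaining cobimetinib could describe only the one restart after the first recurrence. Step e names the end state, so a site could infer that single-level cuts continue until it is reached. The order b-d-b-d gives 960/40, 720/40, 720/20, 480/20, with the stop at episode 5. Row D leaves its second cut implicit too, and row G describes one step while its example covers both vemurafenib levels.

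Part of this stands. Whether the gap opens at episode 3 or episode 4 depends on whether step d is used once or repeatedly, and the text does not say. If step d is single-use, it is weaker ground for ruling out a return to step b. But no written step orders the 40 to 20 mg cut on either reading, and the only text on cobimetinib after a recurrence says to keep the dose. Row D has no such sentence.

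The safeguards are also real. Step b stops both drugs if there is no improvement by 28 days. Section 4.6.1.1 requires stopping for intolerance despite protocol-defined reduction. Section 4.6.1 lets the investigator stop study drug at any time, and Table 10 yields to clinical judgment. A reader might infer that patients are trapped on treatment with no way to stop; these provisions rule that out. They do not make the row consistent, and the intolerance rule itself leans on a reduction sequence that row E leaves incomplete.

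A reader might also infer from the missing letter c that a step was lost. The text cannot settle this: the second bullet under b may be the old c. The point does not depend on it.

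**Conclusion.** Row E is internally inconsistent. From 960/60 its steps reach 720/40, or 480/40 if step d repeats, while its permanent stop requires 480/20. The second cobimetinib reduction is never ordered, and the sentence maintaining its dose blocks it.

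The size is small. The reported 6.5% with any Grade 3 or 4 diarrhea bounds those combination patients who could start down this path, and few of them are likely to have three or four such episodes. That figure does not cover later events or control patients after crossover, whose starting cobimetinib dose is assumed here to be 60 mg.

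Two stronger readings are not supported. The stopping pair is not unreachable for everyone, since reductions made for other toxicities can bring a patient to it. The trial's efficacy findings are not touched either. Label: wrong as written, minor.

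**What to change.** Limit step d's instruction to maintain cobimetinib to the first recurrence, and add a step before step e along these lines:

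*If Grade ≥3 diarrhea recurs again, hold both drugs until Grade ≤1. If this is reached within 28 days, restart with a further one-level reduction of a drug not yet at its lowest level (cobimetinib 40 to 20 mg, vemurafenib 720 to 480 mg). Otherwise discontinue both. This step also applies when one drug is already at its lowest level.*

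The sponsor should state the order of the cuts, or choose a joint cut. Either is a dosing decision that the protocol does not settle. The last sentence matters: without it, a patient who arrives at 480/40 from 480/60 would still have no instruction. Step e then applies on recurrence at 480/20, and the row should be re-lettered.

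If the sponsor intends an earlier stop, restate step e's trigger as the lowest dose pair the written steps reach: from full dose 720/40, or 480/40 if step d is meant to repeat.

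The cost is a correction to one table row and a letter to sites.

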#### **5.1.4.6 Hepatic Toxicity**

Grade 4 elevations of serum  $\gamma$  glutamyltransferase and other less severe liver function abnormalities have been reported in patients treated with vemurafenib and cobimetinib. These have generally been managed with interruption of treatment and dose reduction. All patients will undergo liver function testing (AST, ALT, total bilirubin, ALP, and  $\gamma$  glutamyltransferase) at periodic intervals while on study treatment (see [Appendix 1](#)). Guidelines for interruption/dose modification in the setting of liver function abnormality are provided in [Table 10](#).

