Table 10 Management of Specific Toxicities and Dose Modification Guidelines (cont.)	
Adverse Event	Action
J) Other Grade 4, non-hematologic adverse events related to study drug (except for GGT or CPK elevation)	
a) Interrupt dosing of vemurafenib and cobimetinib.
 
b) If adverse event resolves to Grade <math>\leq 1</math> within 28 days, then restart dosing of vemurafenib and cobimetinib. Vemurafenib should be decreased by 2 dose levels and cobimetinib by 1 dose level.
 
c) If the adverse event does not resolve to Grade <math>\leq 1</math> by 28 days, discontinue study treatment.
 
d) If the Grade 4 adverse event recurs (a second time), then both agents should be discontinued.

Hemorrhage	
Grade 3 events: Interrupt cobimetinib treatment. There are no data on the effectiveness of cobimetinib dose modification for hemorrhage events. Clinical judgment should be applied when considering restarting cobimetinib treatment. Vemurafenib dosing can be continued when cobimetinib treatment is interrupted, if clinically indicated.
 
Grade 4 events or cerebral hemorrhage (all grades): Interrupt cobimetinib treatment. Permanently discontinue cobimetinib for hemorrhage events attributed to cobimetinib.

ADL = activities of daily living; BID = twice daily; CPK = creatine phosphokinase; cuSCC = cutaneous squamous cell carcinoma; EF = ejection fraction; GGT =  $\gamma$  glutamyltransferase; LFT = liver function test; LLN = lower limit of normal; LVEF = left ventricular ejection fraction; NCI CTCAE = National Cancer Institute Common Terminology Criteria for Adverse Events; QD = once daily; QTc = corrected QT interval; RVO = retinal vein occlusion; SCC = squamous cell carcinoma

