### **5.2.3 Adverse Events of Special Interest (Immediately Reportable to Roche)**

Adverse events of special interest are required to be reported by the investigator to the Sponsor immediately (i.e., no more than 24 hours after learning of the event; see Section 5.4.2 for reporting instructions).

Adverse events of special interest for this study include the following:

- Any retinal vein occlusion
- Any retinal detachment, retinal pigment epithelium detachment, neurosensory retinal detachment or *central serous chorioretinopathy*
- Grade  $\geq 3$  photosensitivity
- Grade  $\geq 3$  rash
- Grade  $\geq 3$  elevations of AST, ALT, serum bilirubin,  $\gamma$  glutamyltransferase, or cases of elevated ALT or AST in combination with either an elevated bilirubin or clinical jaundice, as defined in Section 5.3.5.6
- Grade  $\geq 3$  QT interval prolongation

- Cardiac events/ Grade  $\geq 2$  LVEF reduction
- Any cutaneous primary malignancy, including squamous cell carcinoma (SCC), keratoacanthoma (KA), basal cell carcinoma (BCC), new primary melanoma.
- *Suspected transmission of an infectious agent by the study drug, as defined below*  
*Any organism, virus, or infectious particle (e.g., prion protein transmitting transmissible spongiform encephalopathy), pathogenic or non-pathogenic, is considered an infectious agent. A transmission of an infectious agent may be suspected from clinical symptoms or laboratory findings that indicate an infection in a patient exposed to a medicinal product. This term applies only when a contamination of the study drug is suspected.*

The occurrence of any cutaneous primary malignancy, including SCC, KA, BCC, new primary melanoma will be considered a Grade 3 adverse event in this study. Any non-cutaneous primary malignancy will be reported as a serious adverse event (see Section 5.2.2).

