#### **5.3.5.6 Abnormal Liver Function Tests**

The finding of an elevated ALT or AST ( $>3 \times$  baseline value) in combination with either an elevated total bilirubin ( $>2 \times$  ULN) or clinical jaundice in the absence of cholestasis or other causes of hyperbilirubinemia is considered to be an indicator of severe liver injury. Therefore, investigators must report as an adverse event the occurrence of either of the following:

- Treatment-emergent ALT or AST  $>3 \times$  baseline value in combination with total bilirubin  $>2 \times$  ULN (of which 35% is direct bilirubin)
- Treatment-emergent ALT or AST  $>3 \times$  baseline value in combination with clinical jaundice

The most appropriate diagnosis or (if a diagnosis cannot be established) the abnormal laboratory values should be recorded on the Adverse Event eCRF (see Section 5.3.5.1) and reported to the Sponsor within 24 hours after learning of the event, either as a serious adverse event or an adverse event of special interest (see Section 5.4.2).

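### Table 10 row G sets liver dosing by grade alone, with no exception for the ALT/AST-plus-bilirubin (or jaundice) combination that Section 5.3.5.6 treats as a sign of severe liver injury

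*Protocol*

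**What the plan says.** Section 5.1.4.6 places all liver dosing rules in one table: "Guidelines for interruption/dose modification in the setting of liver function abnormality are provided in" Table 10. Row G of that table (LFT elevations) has four steps:

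- (a) "If Grade ≤2, continue current dose of vemurafenib and cobimetinib".
- (b) "If Grade 3, hold vemurafenib. Continue current dose of cobimetinib". Vemurafenib resumes one dose level lower once the test is back to Grade ≤1.
- (c) Grade 4 is referred to row J, whose title begins "Other Grade 4, non-hematologic adverse events related to study drug (except for GGT or CPK elevation". Row J interrupts both drugs.
- (d) An isolated GGT rise needs no dose change.

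Section 5.3.5.6 defines a combination: ALT or AST above 3 times baseline, together with total bilirubin above 2×ULN or "clinical jaundice in the absence of cholestasis or other causes of hyperbilirubinemia is considered to be an indicator of severe liver injury". The step it attaches is to record the event and report it within 24 hours. On recording it says: "The most appropriate diagnosis or (if a diagnosis cannot be established) the abnormal laboratory values should be recorded".

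Section 5.2.3 lists this combination among the adverse events of special interest beside Grade ≥3 liver test elevations: "or cases of elevated ALT or AST in combination with either an elevated bilirubin or clinical jaundice, as defined in Section 5.3.5.6".

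**The concern.** The protocol singles out one liver pattern as a marker of severe injury and defines it relative to the patient's own baseline, not by grade. The dosing table looks only at grade. The two scales need not agree, and where they disagree the written dosing instruction is to carry on with one drug or both.

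What is at stake is patient safety in a rare situation. A site that follows row G literally could keep a patient who meets the Section 5.3.5.6 definition on cobimetinib, and possibly on both drugs. Section 5.1.2.2 lists severe hepatotoxicity under the potential risks of cobimetinib, so the drug that continues at Grade 3 is not one the protocol regards as free of liver risk.

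Not every event of special interest needs its own dosing rule. Grade ≥3 GGT is one, and row G reasonably leaves it alone when isolated. The difference here is the label that the protocol itself gives the combination.

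**Working it through.** There is no planned figure to reproduce. The check compares sections and then asks which grades the combination can take.

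**1. Is there a hold anywhere else?**

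| Place | What it does for the combination |
|---|---|
| Table 10 row G (a), (b) | Continue both; hold vemurafenib only |
| Table 10 row G (d) | Exempts isolated GGT; loosens the rule |
| Table 10 row J | Interrupts both, but only for Grade 4 events related to study drug |
| 5.3.5.6, 5.2.3 | Recording and 24-hour reporting |
| 4.6.1.1 | Mandatory stopping reasons; no liver criterion |
| 5.1.5, 4.6.1 | Clinical judgment kept; investigator may stop drug |
| 5.5.2, 5.7 | Sponsor may follow up and evaluates the event |

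Several of these permit a stop. None directs a hold of both drugs below Grade 4.

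**2. Which grades can the combination take?** Let b be baseline ALT in multiples of ULN. The ALT criterion is ALT > 3b. The CTCAE limits are not in the protocol, so they are assumptions here: L and U are the upper limits of Grade 2 and Grade 3 for ALT, and B is the upper limit of Grade 2 for bilirubin, all in ×ULN. The event is taken to carry the grade of its worst component.

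- ALT stays at Grade ≤2 only if 3b < L, that is b < L/3. L = 5 gives b < 1.67; L = 3 gives b < 1.00.
- Bilirubin must lie above 2 and at or below B. B = 3 gives a window from 2 to 3. B of 2 or less gives none, which leaves only the jaundice criterion.
- ALT stays below Grade 4 only if b < U/3. U = 20 gives b < 6.67; U = 10 gives b < 3.33.

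The entry limits in Section 4.1.1 are 3×ULN, or 5×ULN with liver metastases. At these limits the criterion starts at 3×3 = 9 and 3×5 = 15×ULN. Under U = 20 both are below Grade 4, so ALT can meet the criterion below Grade 4 at every eligible baseline. Under U = 10 this fails for baselines from 3.33 to 5×ULN.

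Example: b = 1.0, ALT 4×ULN, bilirubin 2.5×ULN with 35% direct, no other cause. This meets Section 5.3.5.6. Under L = 5 and B = 3 both values are Grade 2, and step (a) says continue both drugs. Under L = 3 the ALT is above Grade 2; at Grade 3, step (b) says continue cobimetinib.

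**3. Does the recording route matter?** If the site records laboratory values, row G applies. If it records a diagnosis, as Sections 5.3.5.1 and 5.3.5.6 prefer, row G may not apply. Below Grade 4 the table is then silent. Neither route yields a hold of both drugs.

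**4. How long could the instruction stand?** Appendix 1 schedules chemistry and LFTs on Day 1 only from Cycle 4 on. Step (a) asks for no earlier retest, so the next scheduled draw can be about 28 days away.

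**5. Can the table handle such a case?** Row D, for visual symptoms of Grade ≥2, opens with "Interrupt cobimetinib and vemurafenib", requires an eye examination and then acts on the diagnosis. Row I separates symptomatic from asymptomatic LVEF decrease. A liver exception would fit the existing format.

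**The case against.** The strongest reply has five parts.

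- *There is no contradiction.* Section 5.3.5.6 belongs to the recording procedures and row G to dosing. Section 5.1.5 says the guidelines do not replace clinical judgment, the investigator may stop treatment at any time, and the sponsor hears within 24 hours. This stands as far as it goes: nobody is forced to continue dosing. But these provisions only allow a departure from row G; the rule itself still says continue.
- *The Grade ≤2 case is conditional.* This stands. It depends on unprinted limits and on the site recording laboratory values.
- *At Grade 3 vemurafenib is held*, and Section 1.2.5.5 reports its drug-induced liver injury cases. Holding one drug first is also the pattern in the rash and QTc rows. That is a defensible choice for ordinary elevations. It does not explain continuing cobimetinib in a pattern labelled severe.
- *The two bullets in 5.3.5.6 omit the condition on cholestasis and other causes*, so a hold triggered by them would catch patients with biliary obstruction or liver metastases. At a baseline of 0.5×ULN, an ALT above 1.5×ULN would meet the first half of the criterion. This stands, and the fix must say how to dose once another cause is found.
- *Exposure is late.* The final OS cutoff was 28 August 2015, and the median onset of vemurafenib liver injury was 44 days. New cobimetinib exposure comes only through crossover. This limits the size of the problem.

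**Conclusion.** The gap is real. Row G has no exception for the Section 5.3.5.6 combination, and below Grade 4 nothing directs a hold of both drugs. At Grade 3 cobimetinib continues. At Grade ≤2 both continue, provided the CTCAE limits allow the combination there.

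Three stronger readings are tempting and not supported:

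- A reader might infer that the protocol definitely keeps both drugs going at Grade ≤2. The grade limits are not printed, and a bilirubin limit of 2×ULN or less would leave only the jaundice criterion.
- A reader might take the 63 cases in about 20,000 vemurafenib patients (Section 1.2.5.5) as the expected rate: 63/20,000 = 0.315%, or 0.00315 × 495 = 1.6 of the 247 + 248 randomized patients. Those are reported serious cases with a trend to a cholestatic pattern, whereas 5.3.5.6 excludes cholestasis. They do not measure the combination.
- A reader might take the Grade ≥3 liver laboratory rates in Section 5.1.2.2 (20.5% versus 15.1%) as patients at risk from the gap. They do not separate out the combination, and the same section says elevations were generally managed effectively.

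The protocol gives no count. Affected patients are probably few and limited to those still on treatment or crossing over. No endpoint or efficacy analysis is touched. This is a safety clarification worth making at the next amendment.

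**What to change.** Add to Table 10, row G:

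*If either Section 5.3.5.6 criterion is met, steps (a) and (b) do not apply: interrupt both vemurafenib and cobimetinib pending prompt evaluation for cholestasis and other causes (e.g., biliary obstruction, liver metastases). If such a cause is found, resume dosing under steps (a) to (c) by grade. If none is found, keep both drugs on hold, contact the Medical Monitor before any restart, and consider permanent discontinuation.*

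The trigger is deliberately wider than the definition of severe injury, because the other causes cannot be excluded until they have been looked for; the second sentence returns those patients to the ordinary rule. The cost is an addition to one table row, with no new scheduled visits or data collection. The downside is a short interruption of both drugs in some patients whose abnormality proves to have another cause, and permanent discontinuation in some of those where none is found.
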